4.3.5 Novartis instructions for rapid notification of serious adverse events

The principal investigator has the obligation to report all serious adverse events to the FDA, IRB, and Novartis Pharmaceuticals Drug Safety and Epidemiology Department (DS&E). All events reported to the FDA by the investigator are to be filed utilizing the Form FDA 3500A (MedWatch Form).

All events must be reported, by [contact]), to Novartis Pharmaceuticals DS&E

Department within 24 hours of learning of its occurrence. This includes serious, related, labeled (expected) and serious, related, unlabeled (unexpected) adverse experiences. All deaths during treatment or within 30 days following completion of active protocol therapy must be reported within 5 working days.

Any serious adverse event occurring after the patient has provided informed consent and until 4 weeks after the patient has stopped study participation must be reported. This includes the period in which the study protocol interferes with the standard medical treatment given to a patient (eg, treatment withdrawal during washout period, change in treatment to a fixed dose of concomitant medication).

Serious adverse events occurring more than 4 weeks after study discontinuation need only be reported if a relationship to the Novartis study drug (or therapy) is suspected.

For Comparator Drugs/Secondary Suspects (Concomitant Medications), all serious adverse experiences will be forwarded to the product manufacturer by the investigator.

4.3.5.1 **Pregnancies**

To ensure patient safety, each pregnancy in a patient on study treatment must be reported to Novartis within 24 hours of learning of its occurrence. The pregnancy should be followed up for 3 months after the termination of the pregnancy to determine outcome, including spontaneous or voluntary termination, details of the birth, and the presence or absence of any birth defects, congenital abnormalities, or maternal and/or newborn complications.

Pregnancy should be recorded on a Clinical Study Pregnancy Form and reported by the investigator to the oncology Novartis Drug Safety and Epidemiology (DS&E) department. Pregnancy follow-up should be recorded on the same form and should include an assessment of the possible relationship to the Novartis study treatment of any pregnancy outcome. Any SAE experienced during pregnancy must be reported on the SAE Report Form.

4.3.5.2 Laboratory evaluations

Pregnancy Test

A serum pregnancy test (β -HCG) is required for all women of child-bearing potential at screening, within 72 hours prior to the first dose of buparlisib. Note: Postmenopausal women must have been amenorrheic for ≥ 12 months in order to be considered "of non-childbearing potential". This should be documented appropriately in the patient's medical history. Additional pregnancy tests should be performed as clinically indicated. Will continue to check pregnancy tests once a month while in study.

Hematology

Hematology includes the following parameters: complete blood count (CBC) consisting of red blood cell (RBCs), a total white blood cell count (WBC) with differential (total neutrophil count including bands, lymphocyte, monocyte, eosinophil, and basophil counts); hemoglobin (Hgb); and platelet count.

Coagulation Profile

The coagulation profile includes prothrombin time or INR, and activated partial thromboplastin time.

Serum chemistry

Biochemistry includes the following parameters: K+, Na+, Ca++, Mg++, LDH, ALT, AST, total bilirubin (direct and indirect), creatinine, creatinine kinase, amylase, GGT, lipase, alkaline phosphatase (fractionated if alkaline phosphatase is Grade 2 or higher), bicarbonate, phosphorus, uric acid, total cholesterol, HDL, LDL, triglycerides, glucose, urea or BUN, albumin, and total protein are required at every visit including baseline and end of treatment. Subsequent assessments always include K+, Na+, Ca++, ALT, AST, total bilirubin (direct and indirect), creatinine, creatinine kinase, alkaline phosphatase, bicarbonate, phosphorus, glucose, urea or BUN, albumin, and total protein BUT, lipase, total cholesterol, HDL, LDL, triglycerides should be obtained on the first day of odd numbered cycles only. C1D1 assessments may be performed up to 72 hours prior to the

scheduled visit. All other draws should occur within 24 hours of the intended visit. Because accurate serum glucose and lipid measurements are required, patients should be fasting at the time of the blood sampling.

Urinalysis

Urinalysis includes macroscopic (protein, glucose, ketones, blood, and specific gravity) and will be performed at screening visit and EOT visit. A microscopic (WBC/HPF, RBC/HPF, and any additional findings) exam need only be performed if the urinalysis result is abnormal. This must be supplemented with laboratory quantification of any potentially relevant abnormalities.

4.3.5.3 Vital signs

Vital sign assessment consists of height (first visit), pulse, blood pressure, respiration rate, temperature and weight. Blood pressure, pulse and respiration rate should be measured on patients after at least 3 minutes in the sitting position as per the visit schedule.

4.3.5.4 Physical examination

Physical examination will be performed which must comprise a total body examination (general appearance, skin, neck, including thyroid, eyes, ears, nose, throat, lungs, heart, abdomen, back, lymph nodes, extremities and basic nervous system). Significant findings made after the start of study drug which meet the definition of an Adverse Event must be recorded. Tumor exam will be done at each visit and will include measurements of single largest diameter of visible tumor or radiographic imaging for tumors that are not clinically visible.

4.3.5.5 Neuropsychiatric assessments

Patient self-rating mood questionnaires for anxiety and depression (PHQ-9, GAD-7) will be applied at:

- **♦♦** Screening
- ◆◆ Days 1 and 15 of Cycle 1
- ◆◆ Day 1 and 15 of Cycle 2
- •• Day 1 of Cycle 3 and subsequent cycles (only for patients who have not shown mood alterations during the first 2 cycles, patients who did should continue to fill out the questionnaire on a weekly base).
- **♦♦** End of Study treatment

Additional assessments may be done according to the clinical judgment of the Investigator. Symptomatic patients (\geq CTCAE Grade 1) must continue with questionnaires on a weekly basis while active on the treatment portion of the study. Instructions on how to instruct the patient to complete the questionnaires as well as how to determine the scores will be provided together with each instrument. This will be done as an online HIPPA compliant survey tool through Stanford.

4.3.5.6 **ECG/ECHO**

A standard 12 lead ECG is to be performed at screening and as clinically indicated. An echocardiogram (ECHO) or MUGA will be performed to assess eligibility. ECHO/MUGA will be repeated at Cycle 4 and then every 4th cycle thereafter.

4.3.5.7 **Performance status**

Performance status will be assessed at screening and per the visit schedule. ECOG will be used for assessment (See Appendix A).

4.3.5.8 Special tests

Chest X-ray

Will be performed at baseline and every 8 weeks for monitoring per standard protocol.

CT scan

Will be performed at baseline, at 4 weeks and every 8 weeks thereafter for tumor assessment of non-visible tumors per RECIST 1.1 protocol. If CT scans show stability after cycle 4, then CT scan to be performed every 12 weeks instead.

Biomarkers

- ◆◆ Tissue samples at baseline, week 12 and 24 (or EOT, whichever occurs first) will be taken and sent for whole exome sequencing, gene expression profiling and immunohistochemistry. Whole exome sequence will include interrogation for DNA mutations in the tumor and peripheral blood. Gene expression analysis will identify increases or decreases in pathways including Hedgehog and PI3K. Immunohistochemistry to quantify protein levels of Gli 1,2, Ptch 1,2, PI3K in semi-quantitative fashion will be performed to confirm expression analysis results.
- ♦♦ Whole exome sequencing and gene expression analysis may identify novel resistance mechanisms in these BCCs that would be useful to inform future clinical trials

5 Investigational agent sampling and shipping information

[name], or her designated associate will receive study medications at the Stanford Investigational Pharmacy, Redwood City, CA.

5.1 Investigational treatment

For this study, the terms "investigational drug", "study drug" or "study treatment" refers to the combination of Sonidegib and buparlisib. If an individual drug is to be referenced the individual name will be present.

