4.1 Dose modification, interruption or discontinuation of treatment

If an adverse event is clearly associated to one of study drugs, the dose adjustment directed for that study drug will be followed; however, if the causality is not clear, then it may be necessary to adjust both study drugs. Dosing adjustments will be discussed with the sponsor. If a patient experiences a DLT then treatment with Sonidegib plus buparlisib must be stopped and the patient may be discontinued from the study. However, following resolution of the DLT to CTCAE Grade 1 or to the patient's baseline value, the patient may continue to receive study treatment with a 50% dose reduction for either sonidegib, buparlisib or both, if appropriate, at the discretion of the investigator and after discussion with the Sponsor.

If a patient requires a dose delay of > 21 days due to an sonidegib- or buparlisibrelated toxicity, then the patient must be discontinued from the study; however, if the patient is obtaining clinical benefit (ie, SD, PR, or CR), the patient may continue treatment at the same or at a reduced dose following discussion between the investigator and Novartis. All patients will be followed for AEs and SAEs for 30 days following the last dose of sonidegib and/or buparlisib. If the administration of study treatment was interrupted for reasons other than toxicity, then treatment with Sonidegib and buparlisib may be resumed at the same dose.

Patients who experience hematologic, renal, hepatic, or muscle toxicities should receive follow up and dosing modifications for sonidegib as per Table 9 and 10 below. Specific instructions for follow-up and dosing modifications for sonidegib are described in detail in Table 9. Patients who experience muscle toxicity, regardless of whether the toxicity meets the criteria described for a DLT, should be receive follow-up and dosing modifications specified in Table 9 below.

Table 9. Recommended dose modifications and dose delays for suspected sonidegib** treatment-related toxicities	
Worst toxicity CTCAE grade* (value)	During a cycle of therapy
Не	ematologic
Neutropenia (ANC)	
Worst toxicity CTCAE grade* (value)	During a cycle of therapy
Grade 1 (ANC < LLN - 1500/mm ³)	Maintain dose level
Grade 2 (ANC < 1500 - 1000/mm ³)	Maintain dose level

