If a patient requires a dose interruption of > 21 days from the intended day of the next scheduled dose because of a sonidegib-related toxicity, then the patient must be discontinued from the study.

*Common Toxicity Criteria for Adverse Events (CTCAE Version 4.0).

** If the investigator deems that a recommended dose reduction or the recommendation to maintain the same dose level is not in the best interest of the patient, this decision may be discussed with Novartis on a case-by-case basis.

Criteria for follow-up and dosing modifications for buparlisib are described in detail in Table 10.

For overlapping toxicities of sonidegib and buparlisib, specifically hematologic, renal and hepatic toxicities, BOTH sonidegib and buparlisib will be reduced or discontinued depending on toxicity grade per the guidelines listed below for each drug (Tables 9 and 10).

Table 10. Recommended dose modifications and dose delays for suspected buparlisib treatment-related toxicities		
Worst toxicity CTCAE grade* (value)	During a cycle of therapy	
	Hematologic	
]	Neutropenia (ANC)	
Grade 1 (ANC < LLN - 1500/mm ³)	Maintain dose level	
Grade 2 (ANC < 1500 - 1000/mm ³)	Maintain dose level	
Grade 3 or 4 (ANC < 1000 - 500/ mm ³ or < 500/mm ³)	 Omit dose until resolved to ≤ Grade 1, then: If resolved in ≤ 7 days, implement 50% dose reduction If resolved >7 days, discontinue drug If a Grade 4 event, consider hospitalization if appropriate 	
Thrombocytopena		
Grade 1 (PLT < LLN - 75 x 10 ⁹ /L)	Maintain dose level	
Grade 2 (PLT < 75 - 50 x 10 ⁹ /L)	Maintain dose level	

Grade 3 (PLT $< 50-25 \times 10^9/L$)	Omit dose until resolved to ≤ Grade 1, then:	
	 If resolved in ≤ 7 days, then maintain dose level If resolved in > 7 days, then implement 50% dose reduction 	
Grade 4 (PLT < 25 x 109/L)	Omit dose until resolved to ≤ Grade 1, then implement 50% dose reduction. Consider if hospitalization is appropriate	
	Renal	
	Serum creatinine	
Serum creatinine <1.5 x ULN	Maintain dose level	
Serum creatinine 1.5-3 x ULN	Omit dose until resolved to ≤ Grade 1, then: •• If resolved in ≤ 7 days, then maintain dose level •• If resolved in > 7 days, then implement 50% dose reduction (consider checking serum CK, if not already done)	
Table 10. Recommended dose modifications and dose delays for suspected buparlisib treatment-related toxicities		
Worst toxicity CTCAE grade* (value)	During a cycle of therapy	

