Grade 3 Serum creatinine > 3.0 - 6.0 x ULN	Omit dose until resolved to ≤ Grade 1 then implement 50% dose reduction	
Grade 4 Serum creatinine > 6.0 x ULN	Omit dose and discontinue study drug. Consider hospitalization if appropriate	
Hepatic		
Bilirubin (*for patients with Gilbert syndrome these dose modifications apply to changes in direct bilirubin only) will be fractionated if elevated		

Total bilirubin <1.5 x ULN	Maintain dose level
T . 1177 1: 150 IV	Omit dose until resolved to \leq Grade 1, then:
Total bilirubin 1.5-3 x ULN	◆◆ If resolved in ≤ 7 days, then maintain dose level
	◆◆ If resolved in > 7 days, then implement 50% dose
	reduction
Condo 2	Ourit dans until manhand to < Conda 1 than
Grade 3	Omit dose until resolved to ≤ Grade 1, then implement 50% dose reduction
Total bilirubin > 3.0 - 10.0 x ULN	implement 30% dose reduction
Grade 4	Discontinue study medication
Total bilirubin > 10.0 x ULN	Consider if hospitalization is appropriate
	AST or ALT
Grade 1 (> ULN - 3.0 x ULN)	
	Maintain dose level
Grade 2 (> 3.0 - 5.0 x ULN)	Maintain dose level
Grade 3 (> 5.0 - 20.0 x ULN)	Omit dose until resolved to < Grade 1 or baseline then:
	♦♦ If resolved in \leq 7 days, then maintain dose level
	◆◆ If resolved in > 7 days, then implement 50% dose
	reduction
Grade 4 (> 20.0 x	Discontinue study drug
ULN)	Consider if hospitalization is appropriate
AST or	ALT and concurrent Bilirubin
AST or ALT > 3.0 x ULN and	Discontinue study drug
total bilirubin > 2.0 x ULN	

*(LFTs include albumin, ALT, AST, total bilirubin (fractionated if total bilirubin > 2.0 x ULN), alkaline phosphatase (fractionated if alkaline phosphatase is Grade 2 or higher) and GGT). Monitoring (*for patients with Gilbert Syndrome: total and direct bilirubin must be monitored, intensified monitoring applies to changes in direct bilirubin only; the monitoring includes the following LFTs: albumin, ALT, AST, total bilirubin (fractionated if total bilirubin > 2.0 x ULN), alkaline phosphatase (fractionated if alkaline phosphatase is Grade 2 or higher) and GGT).

In case of any occurrence of ALT/AST/ bilirubin* increase ≥ **Grade 2** the liver function tests must be monitored **weekly** or more frequently if clinically indicated **until resolved to** ≤ **Grade 1**

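### The Section 5.1 definition of study drug clashes with the drug-by-drug dose tables, Table 9 lacks a row for combined AST/ALT and bilirubin elevation, and Table 10's footer names sonidegib

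*Combined protocol and SAP*

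**What the plan says.** Section 5.1 sets the terminology: the unnamed term *study drug*, like its synonyms there, "refers to the combination of Sonidegib and buparlisib. If an individual drug is to be referenced the individual name will be present".

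Section 4.1 works drug by drug. If an event is clearly due to one agent, "the dose adjustment directed for that study drug will be followed". The text before Table 10 says "Criteria for follow-up and dosing modifications for buparlisib are described in detail in Table 10"; Table 9 is titled and introduced as the sonidegib table. For hematologic, renal and hepatic toxicity, which Section 4.1 lists as overlapping, "BOTH sonidegib and buparlisib will be reduced or discontinued depending on toxicity grade per the guidelines listed below for each drug (Tables 9 and 10".

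The liver rows are:

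- **Grade 4 AST/ALT (above 20 × ULN).** Table 9 holds the dose until recovery, then resumes at 50%. Table 10 discontinues *study drug*, with no drug named.
- **Combined elevation.** Table 10 has a row that begins "AST or ALT > 3.0 x ULN and" and adds total bilirubin above 2.0 × ULN. The action is again to discontinue *study drug*. Table 9 has no such row.

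Elsewhere Table 10 does name buparlisib when it stops treatment: LVEF Grades 3 and 4, Grade 4 rash and Grade 4 fatigue. Its closing notes concern sonidegib: they end sonidegib if a dose-limiting toxicity recurs after a reduction, and apply a 21-day limit to sonidegib-related toxicity.

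**The concern.** Two rules decide what the unnamed drug in Table 10 means, and they give different sonidegib actions after serious liver events. If 5.1 governs, both drugs stop. If table scope governs, only buparlisib stops, and Table 9 decides what happens to sonidegib.

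On the table-scope reading the combined elevation exposes a gap. The protocol treats it as serious enough to end buparlisib, yet gives sonidegib no corresponding instruction. The event cannot be assumed to be due to buparlisib alone. Hepatic toxicity is listed as overlapping, AST increase was a dose-limiting toxicity of sonidegib in its first-in-human study (Section 1.4.7.2.1), and Section 4.3.3 attributes events to the combination unless another cause is clear.

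The Table 10 footer is a separate slip with a direct dosing consequence: read as written in the buparlisib table, it withdraws the other drug. What is at stake is the safety of individual patients, not the estimation of the response rate.

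**Working it through.** The plan states no figure on this point, so the check is a side-by-side reading, followed by a count.

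**Step 1. Sonidegib action under each reading**

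| Event | Table 10 read through 5.1 | Table-scope reading (4.1) |
|---|---|---|
| Grade 4 AST/ALT | stop sonidegib | hold, then 50% |
| AST/ALT > 3 and bilirubin > 2 × ULN | stop sonidegib | separate Table 9 rows only |

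**Step 2. Which reading is better for Grade 4 AST/ALT.** The overlap rule is specific to hepatic toxicity and points each drug to its own guideline. The treatment sections do not follow 5.1 either: 4.1 and 4.2.1 use study drug for one agent. Within Table 10, a literal 5.1 reading would stop both drugs for Grade 3 rash or fatigue but only buparlisib for Grade 4, which is hard to believe was meant. One sentence in 4.1 does cut the other way, sending sonidegib adjustments for hepatic toxicity to both tables, but the next sentence points to Table 9. Table scope is the better reading, and 5.1 contradicts it.

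**Step 3. Combined elevation on the table-scope reading.** Inputs from Table 9:

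- Total bilirubin 1.5–3 × ULN: hold, then full dose if resolved in 7 days or less, otherwise 50%. Above 3–10: hold, then 50%. Above 10: discontinue.
- AST/ALT above 3–5 × ULN: maintain. Above 5–20: hold, then full dose if resolved in 7 days or less, otherwise 50%. Above 20: hold, then 50%.

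The stricter row is applied, following the instruction to go by the worst preceding toxicity.

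| Bilirubin (× ULN) | AST/ALT > 3–5 | AST/ALT > 5–20 | AST/ALT > 20 |
|---|---|---|---|
| > 2–3 | full or 50% | full or 50% | 50% |
| > 3–10 | 50% | 50% | 50% |
| > 10 | stop | stop | stop |

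Sonidegib may restart in 2 + 4 = 6 of 9 cells and stops in 3. Full dose is possible in 2. Table 10 discontinues in all 9. These are cells of a grid, not probabilities.

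**Step 4. Does another clause settle it?**

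- Dose-limiting toxicity (4.1): both drugs stop, but after resolution "the patient may continue to receive study treatment with a 50% dose reduction for either sonidegib, buparlisib or both". I found no list of the liver events that count. If the combined event were handled as dose-limiting, this clause offers resumption at 50%, not at full dose.
- 21 days: 4.2.1 ends all treatment after a buparlisib delay of more than 21 days, without saying whether permanent discontinuation is a delay. Section 4.1.1 has a similar rule. Section 4.1 makes an exception for clinical benefit: "the patient may continue treatment at the same or at a reduced dose following discussion between the investigator and Novartis".
- Table 9 footnote: where the investigator thinks a recommended action is not in the patient's interest, "this decision may be discussed with Novartis on a case-by-case basis".

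These clauses may limit a restart. None states the sonidegib action.

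**Step 5. Frequency.** The rate of either event at sonidegib 200 mg plus buparlisib 80 mg is not given. As context, Table 6 reports Grade 3–4 liver toxicity of any cause at buparlisib 100 mg: (13 + 4 + 6 + 2 + 0)/(55 + 9 + 50 + 12 + 6) = 25/132 = 18.9% (exact 95% CI 12.6% to 26.7%). If that rate applied to the 24 planned patients, the expected number would be 24 × 0.189 = 4.5 (3.0 to 6.4 from the CI limits). Under that assumption this is an upper limit for Grade 4 AST/ALT, because grades and tests are pooled. It is no limit for the combined event, which can be met at Grade 2. Section 1.5.2.2.1 reports no Hy's law case so far.

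**The case against.** The strongest reply is that the specific rule already governs. The overlap rule sends each drug to its own table, and 5.1 sits in a section on drug sampling and shipping. A reader might infer that no sonidegib action exists for Grade 4 AST/ALT. The documents do not support that: Table 9 states one. This part of the objection stands, and what remains there is a contradicting definition, not an omission.

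A reader might also picture two investigators treating the same event in opposite ways. Section 3.1 describes a single-center study, and 4.1 says that dose adjustments will be discussed with the sponsor, so this risk is small. Table 9's actions are recommendations, and 4.3.3 lets the investigator stop for intolerable toxicity. If the 4.2.1 rule covers permanent discontinuation, sonidegib ends anyway, subject to the clinical-benefit exception. All of this reduces the harm. None of it supplies a default action for the combined event.

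It is tempting, too, to call buparlisib the wrong drug in Table 9's Grade 2 row for other cardiac events. Table 10 has the same wording for that row, and Section 1.4.2 reports no cardiac muscle toxicity with sonidegib in its phase 1 trial, so it may be intended. The Table 10 footer is different. It repeats Table 9's sonidegib text inside the buparlisib table, and no reason for that is given.

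**Conclusion.** The point holds as a minor to moderate safety clarification, in three parts:

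1. Section 5.1 contradicts the drug-by-drug use of Tables 9 and 10, and Table 10's mixed wording keeps the literal reading alive.
2. On the better reading, Table 9 has a gap for the combined elevation. It permits a sonidegib restart for bilirubin up to 10 × ULN. A full-dose restart is open when bilirubin is above 2–3 × ULN, AST/ALT is at most 20 × ULN and the event resolves within 7 days.
3. Table 10's footer stops the wrong drug for its table.

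Part 2 assumes table scope, the stricter Table 9 row, and that the event is not handled under the dose-limiting-toxicity clause. The combined event is probably rare, and its rate on this regimen is unknown. The documents do not require sonidegib to stop after it; stopping is a recommendation based on the overlapping hepatic toxicity. Nothing here affects the response rate.

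**What to change.** - Name the drug in each Table 10 action cell, and exempt Tables 9 and 10 from the 5.1 definition.
- Add a row to Table 9 for AST or ALT above 3.0 × ULN together with total bilirubin above 2.0 × ULN, with the action to discontinue sonidegib. If the sponsor prefers a restart, the row should give its dose and conditions.
- Change the drug in Table 10's footer to buparlisib.
- State in Section 4.2.1 whether sonidegib may continue once buparlisib is permanently stopped.
- Ask the sponsor to confirm which drug is meant in Table 9's Grade 2 row for other cardiac events, without presuming an error.

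The cost is a wording amendment with one added row. It needs no extra visits, tests, patients or data. The downside is that a few patients may lose a possible sonidegib restart.
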